2.3.4 STATISTICAL DATA CONTROLLER

[name] [name] (Methodological and Statistical Advisory Group, Department of Medicine, Faculty of Biomedical and Health Sciences), European University of Madrid.

2.4 POPULATION AND CALCULATION OF THE SAMPLE.

The sample will be obtained from patients who are registered in the database of the Polyclinic of the European University of Madrid, who request a Michigan type splint for the treatment of bruxism, made of acrylic, made in two of the usual ways: printed or injected, in accordance with the inclusion and exclusion criteria shown in Appendix I. As the samples were treated with an innovative methodology in the field of dentistry, such as super solvents, this was a pilot study in which two groups of 15 participants each were formed, depending on the manufacturing process of the splint: injected or printed, totaling 30 volunteers.

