Thus, knowing the possible elements identified, the saliva samples can be treated. This is carried out with a volatile supramolecular solvent spontaneously synthesised by adding hexanol and tetrahydrofuran. The methodology to be followed is the same as previously described in the *in vitro* phase.

Dependent variables: substances of very high concern and endocrine disruptors. Independent variables: usual residence, type of manufacture (printed or injected), time, age, type of polymerisation.

After identification and quantification of the detected substances, the data will be collected in a database with the volunteer's information (ANNEX IV).

Finally, the results will be analysed and correlated with those obtained in the experimental laboratory phase, and the possible participating variables: age, type of material, type of manufacture and habits of the participant (figure 2).

[figure not shown]

Figure 2. Timeline of *in vivo* pilot study on substances released from injected or printed acrylic occlusal splints. University Polyclinic of the European University of Madrid.

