2.8 STATISTICAL ANALYSIS

For the descriptive analysis of the variables collected, the mean \pm standard deviation or median [interquartile range] will be used once the distribution has been checked, in the case of the variables collected.

RESEARCH PROTOCOL

quantitative variables. To describe qualitative variables, absolute (n) and relative (%) frequencies will be used and their 95% confidence interval (95% CI) will be calculated.

Chi-square tests (or Fisher's exact tests) will be used to study differences between qualitative variables. In case of quantitative variables, Student's t-test or Man-Whitney U-test will be used, depending on whether they follow parametric or non-parametric behaviour. Binary logistic regression models will be used to determine the Odds ratio (OR) of seroprevalence and its 95% confidence interval (95% CI) to analyse the effect of each variable on the results obtained.

All statistical calculations were performed using SPSS statistical software (version 25.0 IBM Corp.; USA). Statistically significant differences were assumed to exist if the p-value obtained was less than or equal to 0.05.

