ANNEX IV

Voluntary code	CONCENTRATIONS	CONCENTRATIONS	CONCENTRATIONS	CONCENTRATIONS
	M. Saliva 0	M. Saliva 1	M. Saliva 2	M. Saliva 3
SUBSTANCES				

 Name, surname, ID number and signature of the researcher _____
Date

Sample collection table for each volunteer

VARIABLES	Volunteer 1	Volunteer 2	Volunteer 3	Volunteer 4	Volunteer 5
AGE	-				
GENDER (MALE, FEMALE, OTHER)					
MATERIAL (ACRYLIC)					
MANUFACTURING (INJECTED or PRINTED)		-			
USUAL RESIDENCE (URBAN, RURAL)			-		
EXPOSURE TIME (HOURS) BRUXIST (YES/NO)				-	
REFLUX (YES/NO)					
ANTIDEPRESSANTS (YES/NO)					
ANTIHISTAMINES (YES/NO)					
DECONGESTANTS (YES/NO)					

BIBLIOGRAPHY

- Alhazzawi, T. F. (2016). Advancements in CAD/CAM technology: Options for practical implementation. *Journal of Prosthodontic Research*, *60*(2), 72-84.
<https://doi.org/10.1016/J.JPOR.2016.01.003>
- Alharbi, H. F., Algonaiman, R., Alduwayghiri, R., Aljutaily, T., Algheshairy, R. M., Almutairi, A. S., Alharbi, R. M., Alfurayh, L. A., Alshahwan, A. A., Alsadun, A. F., & Barakat, H. (2022). Exposure to Bisphenol A Substitutes, Bisphenol S and Bisphenol F, and Its Association with Developing Obesity and Diabetes Mellitus: A Narrative Review. *International Journal of Environmental Research and Public Health*, *19*(23).
<https://doi.org/10.3390/ijerph192315918>
<https://doi.org/10.1016/J.ADDMA.2020.101693>
- Bisphenol A and incisor molar hypomineralisation:: A review - Dialnet* (n.d.). Retrieved June 17, 2023, from <https://dialnet.unirioja.es/servlet/articulo?codigo=7998248>
- Carneiro Pereira, A. L., Bezerra de Medeiros, A. K., de Sousa Santos, K., Oliveira de Almeida, É., Seabra Barbosa, G. A., & da Fonte Porto Carreiro, A. (2021). Accuracy of CAD-CAM systems for removable partial denture framework fabrication: A systematic review. *Journal of Prosthetic Dentistry*, *125*(2), 241-248.
<https://doi.org/10.1016/j.prosdent.2020.01.003>

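### Section 2.8 plans logistic odds ratios for every recorded variable in 30 volunteers: a joint model would be far overfitted, and single-variable models would mostly converge but be very imprecise, with sparse characteristics often failing

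*Protocol*

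**What the plan says.** Section 2.8 names binary logistic regression as the tool for odds ratios with 95% confidence intervals, and gives its purpose as "to analyse the effect of each variable on the results obtained". Significance is set at p ≤ 0.05. The text does not say whether each variable has its own model or all enter together.

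Section 2.4 fixes the size: "two groups of 15 participants each were formed", "totaling 30 volunteers". The study is called a pilot, and no power, effect size or detection rate is given.

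The variables to be studied are listed three times, differently:

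- Section 2.6, first list: "Independent variables: usual residence, type of manufacture (printed or injected), time, age, type of polymerisation".
- Section 2.6, later: "the possible participating variables: age, type of material, type of manufacture and habits of the participant".
- Annex IV: age, gender, material, manufacture, residence, exposure hours, bruxist, reflux, antidepressants, antihistamines and decongestants.

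Only age and manufacture appear in all three. Objective 5 (section 1.4) asks for the results to be related to process, stage, time, habits and individual characteristics.

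**The concern.** Ordinary maximum-likelihood logistic regression needs enough people in the rarer outcome class for each coefficient. When a covariate, or a combination of covariates, splits the outcome perfectly, the data are separated: the estimated odds ratio is infinite or zero and its Wald interval is meaningless. Thirty people and a list of mostly binary characteristics, several of them probably uncommon, is the setting in which this happens.

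What is at stake is Objective 5. Its results on residence, reflux and medication could be inestimable, or could be published as odds ratios with a p-value although the data barely constrain them. The dependent variables are plural, so the problem would recur for each substance analysed as detected or not detected.

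**Working it through.** The plan gives no figure to reproduce beyond 2 × 15 = 30.

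**Inputs from the protocol.** N = 30, 15 v 15 (section 2.4). Eleven person-level variables (Annex IV). Material has one level, acrylic. Everyone requests the splint for bruxism (section 2.4), so bruxist is near-constant. That leaves 11 − 2 = 9 variables that can vary. Four samples per person give 4 × 30 = 120 samples, but these nine are recorded once per volunteer, so the extra samples add no independent people for estimating them. Time does vary within a person, but it is not one of the nine.

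**Assumptions, because the protocol gives none.** The outcome is substance detected or not; detection is 20, 30 or 50%; all true odds ratios are 1. Two sets of covariate prevalences:
- Sparser: rural 15%, reflux 20%, antidepressants 20%, antihistamines 15%, decongestants 10%.
- Commoner: rural 20%; reflux, antidepressants and antihistamines 30%; decongestants 15%.

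**Step 1. Events per variable, joint model** = 30 × detection / 9.
- 50%: 15/9 = 1.7. This is the ceiling, whatever the detection rate.
- 30%: 9/9 = 1.0.
- 20%: 6/9 = 0.7.

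**Step 2. Separation, joint nine-variable model** (simulated datasets, linear-programming test for complete or quasi-complete separation).

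| Detection | Sparser | Commoner |
|---|---|---|
| 50% | 64% | 29% |
| 30% | 80% | 55% |
| 20% | 91% | 75% |

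The low end moves with the exact prevalences called common: other such choices gave 26% to 36% at 50% detection.

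**Step 3. One model per variable.** A binary covariate separates when its 2 × 2 table has an empty cell. With m exposed out of 30 and detection p, P(no empty cell) = [1 − p^m − (1−p)^m] × [1 − p^(30−m) − (1−p)^(30−m)], averaged over m ~ Binomial(30, prevalence). For manufacture, m is fixed at 15. Probability of an empty cell:

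| Covariate | 20% detection | 30% | 50% |
|---|---|---|---|
| Manufacture, 15 v 15 | 7% | 1% | 0% |
| Prevalence 30% | 17% | 6% | 1.5% |
| Prevalence 20% | 30% | 17% | 8% |
| Prevalence 10% | 59% | 47% | 39% |

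Age and exposure hours separate in about 0 to 1% of fits over this detection range. Averaged over the nine variables with the sparser set, 10%, 15% and 24% of single fits separate at 50, 30 and 20% detection. Most single fits therefore converge.

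**Step 4. At least one of the nine single-variable models fails** (separates, or the covariate is constant).
- Sparser: 66%, 80% and 91% at 50, 30 and 20% detection.
- Commoner: 28%, 50% and 71%.

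**Step 5. Precision of fits that converge.** For 15 v 15, SE(log OR) = √[2/(15p) + 2/(15(1−p))].
- p = 0.5: √(0.267 + 0.267) = 0.730. The 95% interval is the odds ratio divided and multiplied by exp(1.96 × 0.730) = 4.2. The odds ratio detectable with 80% power is exp(2.80 × 0.730) ≈ 7.7.
- p = 0.2: √(0.667 + 0.167) = 0.913, giving a factor of 6.0 and a detectable odds ratio of about 12.9.

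For a 10% covariate (3 v 27) the interval factor is 10.9 at 50% detection and 19.7 at 20%.

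**The case against.** The strongest objection is that section 2.8 speaks of models in the plural and of the effect of each variable, so one model per variable is a natural reading. A reader might infer from the sample size that most fits would separate. On that reading they would not (step 3), and for the balanced manufacture comparison imprecise is the right word. This stands, and it limits the point.

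Second, Annex IV is a data-collection table, and the list that section 2.6 labels as independent variables has only five entries, without reflux or drug classes. A joint model of manufacture, age and residence separates far less often: 15%, 30% and 44% at 50, 30 and 20% detection with 15% rural, and 1%, 9% and 20% with 30% rural. This also stands. However, the three lists disagree and Objective 5 names habits and individual characteristics, so the text does not exclude the wider set.

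Third, one might infer that injected versus printed is the contrast the study was built for, and that it would lose precision through adjustment. The protocol does not support that. Section 2.1 makes the paired before/after comparison central, nothing in the text adjusts manufacture for other variables, and section 2.8 separately provides simple tests.

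Fourth, the outcome is named as seroprevalence, which a saliva study does not measure, and Annex IV records concentrations. If the outcome is corrected to a concentration, the logistic model and this point both lapse.

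Finally, model-building detail can be left to an analysis plan, and a pilot may report imprecise estimates. But the method and its scope are stated here, and a pilot with a descriptive general objective has little reason to test sparse odds ratios at 0.05.

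**Conclusion.** The point holds in conditional form. A joint model of the nine Annex IV variables that can vary has at most 1.7 events per variable, a ceiling that follows from the protocol alone (taking bruxist as constant), and would separate in roughly 30 to 90% of datasets. With one model per variable, most fits converge with very wide intervals. Residence, reflux and the drug classes separate in roughly 1 to 60% of fits, depending on how rare they are, and at least one variable fails in about 30 to 90% of datasets. Material has no estimable odds ratio on either reading, and bruxist almost certainly none.

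Every separation rate rests on assumed detection (20 to 50%), assumed covariate prevalences (10 to 30%), null effects and a binary outcome the protocol does not define. The ranges, not any single value, are the result. A claim that most fits separate whichever way the text is read would go too far.

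**What to change.** In section 2.8, for any substance analysed as detected/not detected:

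- State that no joint model of all Annex IV variables will be fitted.
- Limit any model to manufacture plus at most the Time 0 result, fitted by Firth-penalised or exact logistic regression.
- Drop material and bruxist from the odds-ratio analysis.
- Report sparse characteristics (residence, reflux, drug classes) as counts by detection status.
- Label any other single-variable odds ratio exploratory, and fit it by Firth or exact methods too. Prohibiting these altogether is not necessary.

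Use one variable list in sections 2.6 and 2.8 and Annex IV.

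The cost is wording only; no visit or sample changes. The individual-characteristics part of Objective 5 becomes largely descriptive, and Firth or exact fitting may need an add-on to the software named in section 2.8.

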1.3 JUSTIFICATION

This study is framed within the European Community framework on substances that can have an impact on the health and well-being of the population, focusing on their identification, quantification, monitoring and prevention. The population susceptible to treatment of this kind is almost universal. Companies are investing in improvements in this respect, incorporating substitutes to bisphenols, with effects yet to be confirmed, generating a very dynamic and growing market. The literature demands more solid results and improvements in protocols. The Supramolecular Analytical Chemistry (SAC) research group at the University of Cordoba has developed an innovative, sustainable, specific and more economical method based on the use of supramolecular solvents (SUPRAS) combined with high performance liquid chromatography-high performance mass spectrometry (HPLC-HRMS/MS). This method allows the identification of compounds (known and unknown) by covering a wider range of substances present in the materials under study than solvents.

organic waste cannot be dealt with. Given that this method has not yet been implemented in dentistry, despite being amply tested, this pilot study has been developed to lay the foundations of a protocol, and to have a more exact and extensive knowledge of our treatments. One of the most widely used, especially after the pandemic, is the Michigan type acrylic splint, as a treatment for bruxism. It is also a removable device, which is used at least 6-8 hours a day, and does not involve the use of additional plastic materials that could be other sources of additives, such as cements, sealants or dental temporaries, as is the case with fixed prostheses. The population eligible for such treatment must have completed their bone and tooth growth (18 years of age or older). In the present study, two forms of manufacture were chosen: conventional and printed. The reason for not choosing the milled ones is because the latter generate more waste, and their mechanical response as well as the patient's preference are not better. Therefore, identifying the substances released by the acrylics, using SUPRAS and HPLC-HRMS/MS, by contrasting the *in vitro* and *in vivo* results, may shed some light on this issue.

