1.4 OBJECTIVES

There is no evidence of release of substances of particular concern, or endocrine disruptors released from Michigan type acrylic occlusal splints.

General objectives: To describe and quantify the values of substances of very high concern (SVHC) or endocrine disruptors (ED) released from printed or injected acrylic Michigan type splints.

Specific objectives:

1. To identify the SEPs and EDs released by Michigan-type splints made by injection or *in vitro* impression technique, simulating oral environment and wear.
2. Identify SEPs and EDs in saliva released from printed or saliva-injected acrylic Michigan type splints before, during and after insertion in the mouth.
3. To quantify the levels of SEP and ED in saliva released from printed or injected acrylic Michigan type splints in saliva before, during and after insertion in the mouth.
4. Contrast the results obtained in the laboratory test with those recorded in the saliva samples of the *in vivo* study.

5. Relate the results to the manufacturing process, stage of exposure, time, habits and individual characteristics of each volunteer.

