2 METHODOLOGY OF THE STUDY

2.1 DESIGN

This is a prospective analytical observational experimental pilot study that aims to analyse the substances of particular concern and endocrine disruptors detected in saliva, released by conventional dental devices, before and after the intervention. They will therefore be paired samples, where the control group will be the same subject, minimising the independent variables: saliva pH, microbiome, salivary flow, habits, occlusal wear, erosion by external agents and saliva.

Saliva sampling shall be carried out in accordance with the conventional protocol RD 1716/2011. The saliva containers shall comply with the requirements of the ISO 6717:2021 standard. They shall be packaged and transported according to the protocol Order JUS/1291/2010 of 13 May. All samples shall be identified with the number assigned to the volunteer, time, material and type of manufacture (processed, machined or printed), and shall be sent to the Chemical Institute for Energy and Environment (IQUEMA). University of Cordoba, where they will be analysed by the SAC group, for subsequent statistical treatment and interpretation.

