2.6 DESCRIPTION OF THE STUDY

2.6.1 VOLUNTEER RECRUITMENT:

The study groups will be formed in accordance with the requirements and inclusion criteria. Each of the subjects will be informed of the purpose and methodology of the project by means of an information document for the volunteer (Appendix II) and must sign the informed consent form provided for this purpose (Appendix III); they may withdraw from participation at any time. The data of the participants will be stored in a clinical history with an individual key number, in accordance with the regulations contained in the current Organic Law 3/2018, of 5 December, on the Protection of Personal Data.

Appointments will be made as follows:

APPOINTMENT 1: A conventional computerised clinical history is taken of the patient, in which data is collected on general health, orofacial and nutritional habits and hygiene. We explain in detail what the treatment consists of: Michigan type relaxation splint (device to prevent tooth wear due to bruxism). Each intervention is governed by scientific and deontological criteria, respecting all the ethical rules of research. The following is a detailed description of the study, its duration and methodology. The four moments of saliva collection will be explained: before, during, and 3 and 6 months after placement, as follows:

-Time 0: the day of the appointment, before the intervention.

-Step 1: On the day of the appointment, device placement.

-Time 2: 3 months after device placement.

-Time 3: 6 months after treatment.

Information and informed consent will be provided.

APPOINTMENT 2: Preparation and taking of models for the Michigan type splint according to the conventional protocol for this treatment.

APPOINTMENT 3: The models will be assembled in the articulator to send and request the making of the splint, specifying whether it is injected or printed.

APPOINTMENT 4: A saliva sample is taken in the device for this purpose. After checking for proper fit and retention, the occlusal adjustments will be made with a handpiece and conventional acrylic and polishing burs. After completion of the procedure, a new saliva sample shall be taken. The samples shall be identified with the patient's assigned code and stored according to conventional standards. An appointment will be made after 6 months to continue with the study and in accordance with the check-up times for correct oral health.

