APPOINTMENT 5: The intraoral check-up will be carried out, checking the intraoral health and the state of the splint, with the pertinent adjustments, according to conventional protocol. A new saliva sample will be taken. The patient will be seen after 3 months.

APPOINTMENT 6: The intraoral check-up will be carried out, checking the intraoral and splint health status, with its pertinent adjustments, according to conventional protocol. A new saliva sample will be taken. The sample collection period for this subject will end.

Prior to this, the substances released by the specific material used to make the devices will be identified in the laboratory. The reason for this is the highly dynamic nature of the dental materials market. For this purpose, the solutions will be analysed by liquid chromatography coupled to a mass spectrometer (LC-HRMS). The identification of the compounds present will be based on a non-directed suspect screening approach, comparing the results obtained in the analyses with those already existing for the

RESEARCH PROTOCOL

compounds included in the

list of suspects. This list shall be compiled on the basis of information gathered during the literature review, among other sources. Thus, it shall include from compounds whose presence is expected such as those indicated by the manufacturer, to emerging compounds that could be present due to storage conditions, use, etc. For the identification, statistical and chemometric techniques will be used to establish the correlation between the analytical signals obtained in the LC-HRMS and the information (e.g. masses, structure, mass spectra, etc.) available in bibliography and publicly available spectrophotometric libraries (e.g. Mass Bank). In a second phase, the compounds identified in the first stage will be prioritised according to their level of identification, frequency of detection, toxicity (if known) and availability of analytical standards. Finally, quantification of these compounds will be carried out (figure 1).

[figure not shown]

Figure 1: Timeline *In vitro* study of acrylic-based dental materials: Resting and weathering phase leaching, identification and quantification of released substances EDs and SEP. SAC innovative research group at the University of Córdoba (Spain) that belongs to the Institute of Fine Chemistry and Nanochemistry (IUNAN).

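### The protocol's only decision rule, p ≤ 0.05 for every test, does not reflect a 30-person descriptive pilot with an open list of substances

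*Protocol*

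**What the plan says.** Section 2.8 names chi-square or Fisher tests, Student's t or Mann-Whitney, and logistic regression for the effect of each variable. It then gives its one decision rule: "Statistically significant differences were assumed to exist if the p-value obtained was less than or equal to 0.05". It plans 95% CIs for frequencies and odds ratios, but not for differences in concentration.

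The scope of the rule comes from other sections:

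- **Substances.** The outcomes are two classes, substances of very high concern and endocrine disruptors. Section 2.6 fills them by suspect screening and then narrows the list: "the compounds identified in the first stage will be prioritised according to their level of identification, frequency of detection, toxicity (if known"). Availability of analytical standards is a further criterion. No maximum number is given.
- **Times.** "The four moments of saliva collection will be explained: before, during, and 3 and 6 months after placement". That is one sample before placement and three from placement on.
- **Factors.** Specific objective 5 in Section 1.4 is: "Relate the results to the manufacturing process, stage of exposure, time, habits and individual characteristics of each volunteer".
- **Release contrast.** Section 2.1: "They will therefore be paired samples, where the control group will be the same subject".

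The status of the study is also stated. Section 1.3: "this pilot study has been developed to lay the foundations of a protocol". Section 2.4: "this was a pilot study in which two groups of 15 participants each were formed, depending on the manufacturing process of the splint". The general objective in Section 1.4 begins: "To describe and quantify the values of substances of very high concern (SVHC) or endocrine disruptors (ED").

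**The concern.** A flat 0.05 threshold suits a single planned test. Here it governs a family of tests whose size depends on how many substances the laboratory phase yields, multiplied by sampling times and by factors. Nothing in Section 2.8 separates a lead for the next study from a difference that the pilot claims to have shown.

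The likely victim is the comparison of manufacturing methods. By following the rule, the report could say that printed and injected splints differ in release of some substance, on the strength of one of many unlabelled tests with 15 people per group. The team commits itself to publication (Section 2.9), and the subject is endocrine disruptors from a widely used device, so such a statement could travel further than the data allow.

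**Working it through.** **Inputs from the protocol.** Threshold 0.05 per test (Section 2.8); 30 people, 15 per manufacturing group (Section 2.4); one sample before placement and three from placement on (Section 2.6.1); Student's t or Mann-Whitney for quantitative variables (Section 2.8). The protocol gives no power or sample size calculation, so there is no derived figure to reproduce.

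**Assumptions.** The number of substances K is not stated; 1, 3, 5 and 10 are used. Tests are two-sided and data normal. The correlation between times within a person is 0.5 to 0.9, and between substances 0 to 0.5. There is no true difference.

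**Step 1: benchmark with independent tests.** Chance of at least one false difference = 1 − 0.95^m, with m = K × 3 times for one contrast.

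- K = 1: 1 − 0.95^3 = 14.3%
- K = 5: 1 − 0.95^15 = 53.7%
- K = 10: 1 − 0.95^30 = 78.5%

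These overstate the figure here, because repeated samples from one person are correlated.

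**Step 2: allow for correlation.** 10,000 studies were simulated per setting, with 30 people, four times and K substances. The table gives the chance of at least one result at p ≤ 0.05.

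| Contrast | K = 1 | K = 3 | K = 5 | K = 10 |
|---|---|---|---|---|
| Printed v injected, 15 v 15, three times, t or Mann-Whitney | 8-13% | 21-34% | 29-50% | 44-75% |
| Each later time v before, n = 30, paired t | 13% | 30-34% | 41-49% | 59-74% |
| The same, counting only increases | 6-7% | 15-18% | 21-28% | 31-49% |
| The same data with an unpaired t-test | 0-2% | 0-6% | 0-9% | 0-17% |

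Repeat runs agree within simulation error; for example, K = 5 printed v injected gave 29% to 49% in one repeat and 31% to 50% in another.

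**Step 3: read the rows.** The first row uses the tests that Section 2.8 names and exceeds 5% even with one substance. The second needs paired tests. If the named two-sample tests are run unpaired on before/after samples, the positive correlation within a person makes them conservative: with 5 substances the figure is 8-9% at correlation 0.5, about 1% at 0.7 and 0% at 0.9. Covariate tests would add to the family, but their number is not fixed and no figure is put on them.

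**Step 4: precision if estimates are reported instead.** 95% CI half-widths:

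- Printed v injected: 2.048 × √(2/15) = 0.75 SD
- Paired before/after: 2.045 / √30 = 0.37 SD of the difference

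**The case against.** Most of what is absent here (a primary substance, a primary time, a multiplicity procedure) is commonly left to a statistical analysis plan, which may exist. The 0.05 threshold is an ordinary convention, and the sentence can be read as merely defining the term 'statistically significant'. The pilot status is stated several times, so few readers would take 15 v 15 for confirmation. The grid of tests is pieced together from several sections, and the substance count is assumed.

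Much of this stands. The absence of a multiplicity procedure is not the point, and the verb in the rule should not be pressed into a claim of proof. What remains is that the protocol itself fixes one unqualified rule for all tests, and a later plan calling them exploratory would have to override it.

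Two stronger readings are tempting, and the document does not support them:

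- A reader might infer that the plan as written will produce false findings of release after placement at the paired-test rates. Section 2.8 names no paired test. Section 2.1 implies one, but if the named tests are run unpaired, the rates are low. That mismatch is a separate matter.
- A reader might infer either that the candidate list is closed before saliva is analysed, or that it is picked from saliva results. Section 2.6 draws the list mainly from the laboratory phase. But specific objective 2 is to identify substances in saliva, and the saliva method is stated to be the same as in the laboratory phase. Additions from saliva are therefore neither planned nor excluded.

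**Conclusion.** The point holds for the manufacture comparison under the tests that the protocol names: about 8-13% chance of at least one false difference with 1 substance, 29-50% with 5 and 44-75% with 10, over three times. It holds for before/after claims only on condition that paired tests are used. The figures rest on assumed substance counts, normal data and the correlation ranges given. The direction does not depend on the count: the manufacture contrast passes 5% with a single substance.

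The severity is minor to moderate. The pilot label and the descriptive aim limit the harm, but the decision rule should say the same as they do.

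**What to change.** Replace the last sentence of Section 2.8 with:

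> This is a pilot study; contrasts by manufacture, time and covariate are exploratory and reported as estimates with 95% CIs, and p ≤ 0.05 is not taken to establish that a difference exists.

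This also supplies the intervals for concentration differences that Section 2.8 does not now promise.

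**Cost.** One sentence, no new data, and no change to any test. Fewer differences can be declared, and the intervals will be wide, as Step 4 shows.

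**Optional, only if the sponsor wants a decision rule for release.** Either name one substance and one post-placement time against the sample before placement, after laboratory prioritisation and before saliva is analysed; or show Benjamini-Hochberg adjusted p-values beside the unadjusted ones, across all substances and the three times, with paired tests. If the adjusted values were used for decisions, simulated power per contrast would fall from 75-76% to 43-45% at a change of 0.5 SD of the difference (1 of 5 substances released). The method controls the false discovery rate, not the chance of any false difference. For a pilot meant to find released substances, that price is a reason to leave it optional.
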